Some of the questions on the scales may seem very personal or embarrassing and fatiguing to participants and may upset them. They may refuse to answer any of the questions that they do not wish to answer. If the questions make them very upset, we will refer them to a social worker.

There is a risk that the video-recordings may be seen by someone they know. It is possible that someone viewing the videos may recognize them, their family members or others and/or hear their names in the audio, and their identities would no longer be confidential. The Care Partners will see each other's' video and audio and share contact information, thus, their identities will not be confidential.

b) Potential Benefits to Subjects

Care Partners who complete all training sessions may experience a reduction in their feelings of burden and depression. They may feel less likely to want to place their care recipients in long-term care. It is possible that these benefits will last up to 6 months. In general, they may feel better about caregiving. Care recipients may experience less psychological stress as their Care Partners learn to communicate and manage behaviors.

Participants who complete seven STELLA-FTD sessions and all other study activities (e.g., surveys) may receive at \$50 ClinCard. We will ask for the participants' social security numbers in order to process the ClinCards.

References

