**Support via technology: Living and learning with advancing
Frontotemporal Degeneration (STELLA-FTD): Phase 2**

NCT # 05338710

03/07/2022

1) Protocol Title

Support via technology: Living and learning with advancing Frontotemporal Degeneration (STELLA-FTD): Phase 2

2) Objectives

The purpose of this study is to test the STELLA-FTD intervention that we designed from end-user feedback in Phase 1. The STELLA (Support via Telehealth: Living and Learning with Advancing Alzheimer's Disease) intervention to specifically address the needs of family Care Partners of persons with frontotemporal degeneration (FTD). STELLA-FTD is a multicomponent video-conference based intervention designed to facilitate effective use of community and peer resources to foster effective management of behavioral and psychological symptoms of dementia. In the STELLA-FTD intervention, professionals ("Guides") meet with family members ("Care Partners") caring for persons with FTD conditions. Working together, the Care Partners and Guides identify strategies to address upsetting behaviors. The goal of this intervention is to reduce upsetting behaviors and thus Care Partner burden. STELLA-FTD has not been tested with families living with FTD and thus, it is not known if it will be helpful to them. **In this study, we will test the new version, STELLA-FTD, to specifically address the needs of family Care Partners for persons with frontotemporal degeneration.**

Aim 1 (Phase 1). Adapt STELLA to the needs of Care Partners for those with FTD

- a. Gather FTD Care Partner feedback on STELLA and suggestions for tailoring STELLA for FTD
- b. Adapt STELLA for FTD Care Partners based on end-user feedback

Aim 2 (Phase 2). Assess the feasibility and acceptability of STELLA-FTD with FTD Care Partners

Aim 3. Assess the preliminary efficacy of STELLA-FTD on the primary outcomes: reducing the frequency of behavioral symptoms and Care Partner *reactivity* to the symptoms as measured on the Revised Memory and Behavior Problems Checklist (RMBPC).¹

3) Background

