Taken together, the literature indicates there are few accessible psychoeducational programs tailored for the unique needs of Care Partners for family members with FTD. Programs that do exist tend to be in the formative stages, require in-person engagement, or are sparsely available, *especially* in the northwestern part of the US. This proposed study addresses these gaps by tailoring the STELLA telehealth intervention specifically for FTD Care Partners.

STELLA was adapted for the well-known STAR-C program.¹⁵ Pilot testing of STELLA prototypes informed revisions, and now STELLA is a telehealth-based, multi-component intervention designed for ADRD Care Partners. STELLA is now being tested on a larger scale, with NIA funding with ADRD Care Partners (R01AG067546). In two pilot studies the STELLA prototype reduced burden in ADRD Care Partners.^{16,17} The qualitative and quantitative data from these studies revealed that the Care Partners felt that it was feasible, acceptable and private. This foundational work indicates that STELLA is primed for modification to meet the unique needs of Care Partners for those with FTD.

4) Study Design

STELLA-FTD is a prospective, mixed methods clinical trial and will occur in two phases. In Phase 1, we gathered FTD Care Partner feedback on STELLA and suggestions for tailoring STELLA for FTD (completed in Fall 2021). We have adapted STELLA for FTD Care Partners based on this feedback. In Phase 2, we will assess feasibility, acceptability and preliminary efficacy of the modified intervention.

STELLA-FTD components and study activities. STELLA-FTD will be adapted from the current STELLA version. Like all STELLA versions, the STELLA-FTD intervention will be provided via videoconferencing and email. *There are no in-person activities.*

Phase 1.

This study employed a convergent mixed-methods design¹⁸ to address the aims. We gathered FTD Care Partner feedback on STELLA and suggestions for tailoring STELLA for FTD through focus groups facilitated by trained STELLA Guides, and elicited written commentary on printed STELLA interventional materials and surveys. We sought Care Partner suggestions for modifications to the intervention so that it meets the unique needs and challenges posed by FTD. The groups were held via videoconferencing. Phase 1 was completed in Fall of 2021.

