The focus groups were conducted with 15 Care Partners (Table 1). The adaptation and revision suggestions from the participants are nested in the intense caregiving experience of living with complex behavioral symptoms, feeling burdened, isolated, and "living in darkness." Focus group participants offered practical suggestions to create a revised STELLA intervention to address the needs of families living with FTD. Three common themes emerged that will frame Phase 2: FTD and

Table 1. Demographics (N=15)	
Age (mean, range, SD)	65.7, 50-79, 8.5
Race (% White)*	86
Gender (% female)*	87
Rural (#, %)	2 (14)
Employed outside home (#, %)	4 (29)
Years caregiving (#, %)	
1-3	3 (20)
3-5	5 (34)
5-7	1 (6)
>7	6 (40)
Diagnosis (#, %)	
BVFTD	4 (27)
FTD	2 (13)
PPA	4 (27)
PSP	1 (6)
Not reported	4 (27)

*n=14

accompanying behaviors lead to burden; it is difficult to get a diagnosis, and finally, there are barriers to participation in caregiver support programs. Care Partners recommended Phase 2 include a roadmap for navigating FTD.

Phase 2

The Revised Intervention. STELLA-FTD will focus on improving participants' ability to a) identify family stressors and b) subsequently use the ABC approach to address the stressors. Identified stressors may include behavioral, cognitive or language symptoms, but could also involve the need for external services (i.e.: speech and language pathology, social work). STELLA FTD will be entirely group-based, without one-to-one sessions.

All meetings will be via telehealth videoconferencing, phone or chat.

5) Study Population

a) Number of Subjects

Phase 2. We will conduct STELLA-FTD with up to 20 FTD family Care Partners.

b) Inclusion and Exclusion Criteria

Inclusion criteria, Phase 2. The Phase 2 sample will be made up of participants who self-identify as a Care Partner for family member, close friend or kin with FTD, primary progressive aphasia, progressive supranuclear palsy or other frontotemporal degenerative dementia. They must speak English and be able to see and hear the videoconference-based interactions. The Care Partner must provide care for the person with FTD. Participants from Phase 1 may choose to enroll in Phase 2, but they are not obligated to do so.

Table 2. Inclusion/Exclusion Criteria, STELLA-FTD Phase 2

Participants	Inclusion	Exclusion

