Care Recipient	
• Diagnosis of FTD or FTD-like dementia.• Family member of Care Partner (this can be a relative, spouse, or close kin that is considered family).• Live in OR, WA, CA, ID, MT, TX and WY.	
• No Frontotemporal Degeneration diagnosis.• Unable to leave Care Partner during STELLA-FTD sessions.
Care Partner	
• Adult caring for family member with FTD-like dementia.• Active or retired family Care Partner (Age 18 years or older).• Speaks and understands English to be able to participate in intervention.• Owns a telephone (smartphone, cell phone or landline).• Has email and mailing address to receive computer, study materials and surveys.• Provides informed consent to participate in the research.	
• Unable to find activity for care recipient during STELLA-FTD sessions to allow Care Partner to work privately with Guide and other Care Partners.• Hearing and/or vision problems severe enough to prevent participation.• Refuses to be video-recorded during STELLA-FTD sessions.• Unwilling or unable to adequately follow study instructions and participate in study procedures.

Care Partners need to provide care for their family member with FTD. Due to COVID and other unforeseen conditions, this care does not need to be in-person. Care Partners experience burden regardless of the location of the person with dementia, thus they do not have to live with them (Table 2).

Care Partners who attend an external support group can participate.

Exclusion Criteria, Phase 2. See Table 2 for detailed Inclusion/Exclusion Criteria. It should be noted that this study includes Care Partners for those with advanced dementia. Thus, it is possible, but not likely, that the care recipient with FTD will die of natural causes while in STELLA-FTD. If this occurs, the Care Partner can remain in the study if he or she chooses to do so.

Care Partners must consent to be video-recorded while in STELLA-FTD sessions. They may turn off their cameras if they prefer.

Once identified, the recruitment team will complete the full screen with potential participants, and if eligible, proceed with the consent procedures (below) with the eligible Care Partners. Screening will be completed using paper or electronic (Qualtrics or REDCap) forms.

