In the event of a screen failure, data collected during screening will be destroyed at the end of the study. The recruitment team will track the number of Care Partners screened for the study, the number consented, the number of those that dropped out, the number who completed some of the intervention, and the number of those that completed the entire intervention.

c) Vulnerable Populations

The primary focus of this study is to assess the acceptability, feasibility and efficacy of the STELLA-FTD intervention. Therefore, in order for this study to be successful, Care Partners of care recipients with FTD will be recruited.

There is a risk of loss of confidentiality if the persons with FTD come into view of the Care Partner's computer screen or if they are overheard on the audio during the STELLA-FTD sessions. Care Partners may discuss their family member with behaviors with other study participants. It may be distressing for the person with FTD if they overhear their Care Partner discussing their family's situation.

To minimize these risks, we will ask Care Partners to identify an activity that will keep the person with FTD (and anyone else) occupied and out of computer range during the weekly, hour-long STELLA-FTD visits.

d) Setting

This study will occur at OHSU. All study activities (screening, consent, intervention, surveys, etc.) will be conducted by the OHSU team.

All study activities will occur via phone, videoconferencing, mail, email and/or text. No in-person visits are required.

e) Recruitment Methods

We will take a multi-pronged approach to subject identification and recruitment which includes working with the Association for Frontal Temporal Degeneration to identify participants. Care Partners may be recruited from clinic sites, ADRC research cohorts, electronic registries, community advisory

committees, faith communities and the community at large. We will reach out to families from We will reach out to families in Oregon, California, Washington, Idaho, Montana, Texas and Wyoming.

Up to 10 of the 20 FTD families enrolled in STELLA-FTD will be recruited from UCSF's ALLFTD study. The ALLFTD team has given our team permission to recruit from this cohort.

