Data from this study may be shared with other investigators for future research studies through the data repository. Data from the repository will be shared with other investigators according to the IRB approved repository policy.

8) Data Analysis

STELLA-FTD will use a mixed-methods approach to assess and refine the intervention. Along with classic quantitative measures, we will engage focus groups to examine program acceptability.

Phase 1. Audio recordings from focus groups were transcribed, and the resulting transcripts were be audited for accuracy and de-identified to remove any personally identifiable information. Dedoose

qualitative software³² was used for data management and coding following the approach of classical content analysis to identify themes.³³ The research team discussed emergent themes, and identified areas of convergence and divergence with survey and demographic data.¹⁸ Findings were used to adapt the STELLA intervention to address the preferences and needs identified from our focus groups.

Phase 2. We will assess data from the surveys to characterize the sample and assess program acceptability. We will compare demographic information, computer use, out-of-pocket costs, health-care usage, behavioral symptom frequency, Care Partner reactivity, burden, depression, and daily activities for those that completed the interventions to those that did not.

For acceptability, we will analyze the STELLA-FTD Experience Survey results using descriptive statistics (mean, range, SD). A directed content analysis approach will be used to analyze the qualitative focus group data. The transcripts from the video recordings may be examined to identify contextual features, Care Partners' goals, the influences of the other Care Partners and Guides and the results the Care Partners experienced. We will identify themes of acceptance, or lack thereof, of STELLA-FTD and the underpinnings of their impressions. These qualitative findings will be considered in relation to the quantitative data using a convergent mixed analysis approach, a widely-used strategy in mixed methods research.¹⁸ This involves separate analyses of the quantitative data (e.g., paired *t* tests, linear regression) and qualitative data, followed by an analysis that looks at areas of data convergence and divergence.

Aim 2 (Establish the efficacy of STELLA-FTD in reducing the *frequency* of behavioral symptoms and Care Partner *reactivity* to the symptoms).

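### Does the Section 8 heading that promises to establish efficacy change what this uncontrolled pilot will conclude?

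*Combined protocol and SAP*

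**What the plan says.** In Section 2 (Objectives), Aim 2 is "Assess the feasibility and acceptability of STELLA-FTD with FTD Care Partners". Aim 3 is "Assess the preliminary efficacy of STELLA-FTD on the primary outcomes", which are RMBPC symptom frequency and Care Partner reactivity. Section 4 (Study Design) agrees about Phase 2: "we will assess feasibility, acceptability and preliminary efficacy of the modified intervention".

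Section 8 (Data Analysis) places the RMBPC analysis under the label Aim 2, with the words "Establish the efficacy of STELLA-FTD in reducing the", followed by frequency and reactivity. The sentence directly below it commits the study to assessing efficacy through pre/post RMBPC change. Regression on change scores and a four-group ANOVA are then offered as options. Paired t tests appear twice: as an example in the mixed-methods paragraph ("This involves separate analyses of the quantitative data") and as an option for depression, extraversion and grief. No confidence interval is named for the RMBPC.

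On design, Section 5a states: "We will conduct STELLA-FTD with up to 20 FTD family Care Partners". Section 6 gives the intervention to all of them. Tables 4 and 5 place the RMBPC at baseline and in the survey due within a week of finishing. Section 5b adds that "Care Partners who attend an external support group can participate".

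**The concern.** Section 8 is the only analysis plan in the document, and its heading gives the primary outcome both a different aim number and a stronger verb than the Objectives do. A reader who opened that section alone could expect a confirmatory result.

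The design cannot deliver one. With no comparator, a change in RMBPC score cannot be separated from the passage of time, outside support or the course of the disease. A larger uncontrolled sample would not cure that.

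The lack of a stated interval adds to the worry. A pilot that aims at preliminary efficacy should report an estimate with its uncertainty, and the methods listed for the RMBPC are either optional or given as examples. At stake is an uncontrolled change being reported as proof that the programme works.

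**Working it through.** **1. The wording, side by side.** Leaving out self-efficacy scales and other programmes, the document refers to the efficacy of STELLA-FTD seven times.

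- Qualified as preliminary, 2: Objectives (Aim 3) and Study Design.
- Unqualified, 5: Section 5c once ("to assess the acceptability, feasibility and efficacy of the STELLA-FTD intervention"), the Section 8 heading once, and the Section 8 text below it three times.

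Of the five unqualified uses, only the heading speaks of establishing efficacy. The other four go with assessing or testing, which is ordinary shorthand once the Objectives have set the qualifier. Two of those four do not bear on the overall RMBPC change: one is about differences between racial and ethnic groups, the other about depression, extraversion and grief.

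**2. Can the heading be misread as another aim?** No. It names frequency and reactivity, the two outcomes of Aim 3. The acceptability analysis stands earlier in Section 8 and the feasibility measures are in Section 6, so the wrong number displaces nothing.

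**3. What depends on the heading?** The documents give no power calculation, alpha, effect size, success threshold or derivation of the 20. There is no stated figure to reproduce and none that the heading could alter.

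**4. Precision of the mean RMBPC change.** Inputs: n = 20 is the stated maximum; 16 and 12 complete pairs are assumptions, as no dropout rate is given; the 95% level is also assumed. In units of the SD of the change score, the half-width is t(0.975, n−1)/√n.

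- n = 20: 2.093/4.472 = 0.47
- n = 16: 2.131/4.000 = 0.53
- n = 12: 2.201/3.464 = 0.64

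These need only the mean, SD and number of pairs. A paired t test, or a regression of change scores on an intercept alone, gives the same interval as routine output.

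**5. Why preliminary is the ceiling.** As an illustration, take n = 20, two-sided alpha 0.05, no intervention effect, and an assumed favourable drift d in SD of change. The chance of a significant improvement is the upper tail of a noncentral t with 19 degrees of freedom and noncentrality d√20.

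- d = 0.2: 13%
- d = 0.3: 25%
- d = 0.5: 56%
- d = 0: 2.5%

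Drift can also run the other way. In a progressive disease, a true benefit of 0.3 SD against a worsening of 0.3 SD nets to zero and leaves the same 2.5%. No drift value comes from the documents. These probabilities belong to any uncontrolled pre/post study of this size and are identical under either heading.

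**The case for a change.** The strongest case for a change is that this is current text, not an amendment log, that results will be reported against Section 8, and that two sections now license different conclusions from the same data. Correcting a heading and adding one reporting sentence would cost almost nothing.

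Part of this stands. The number and the verb are both wrong against the Objectives, the design cannot establish efficacy, and the interval is not written down.

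It does not carry further, because the harm requires someone to read the heading without the sentence beneath it and without the Objectives or Study Design. The Objectives also concede that the programme is untested in families living with FTD and that its usefulness to them is unknown. On the interval, the commitment to pre/post RMBPC change is firm and only the model is optional. Frequency and reactivity are already named as separate targets. Dropout and partial or full completion of the intervention are tracked under Section 5b, and survey completion rates are to be assessed under Section 6, so the number of pairs will be at hand.

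**Conclusion.** No change to the plan is needed. The heading is a clerical slip: one wrong aim number and one verb that is too strong, set against two clear statements that the efficacy aim is preliminary. Correcting it would alter no data, analysis, sample size or decision. The unstated interval is a gap that analysts fill as a matter of course. At full enrolment with complete pairs it would be about ±0.47 SD of the change score, widening to ±0.53 at 16 pairs and ±0.64 at 12.

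This rests on a 95% level, roughly normal change scores and assumed completer numbers. It also rests on the report keeping to the preliminary claim in the Objectives. The absence of a comparator is a true limit on inference, but it is a fair trade-off in a feasibility pilot of up to 20 people, and the protocol's own description of the aim allows for it.

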Efficacy will be assessed by measuring pre/post changes on the RMBPC¹.

We may use linear regression models to examine pre-post changes in primary outcome (RMBPC¹ change scores) utilizing surveys between two points. We may assess relationships between the Care Partner reactivity subscale and the following variables, controlling for age, sex, number of hours caregiving, rural status and education: a. number of STELLA-FTD sessions each Care Partner attended, b. likelihood of placement, and c. out-of-pocket costs.

Using ANOVA, we may assess pre-post changes in the RMBPC (reactivity subscale)¹ between four groups (rural White, African American; urban African American, White), with the hypothesis that there are no significant differences across groups.³⁴ We may test whether the efficacy of our intervention differs across racial and ethnic groups using interaction terms (e.g., time*groups) in linear regression.

We may also assess efficacy in the domains of Care Partner depression,²⁶ extraversion and grief²⁵ before, during and after STELLA-FTD with pre-post paired *t* tests.

If some participants participate by phone only, we may compare their scores with those completing the study via videoconferencing using appropriate statistical measures (e.g., ANOVA).

We may assess the relationships between cost, burden and STELLA-FTD participation using linear regression models and other statistical analyses deemed appropriate for cost analyses.

Other statistical analyses may be completed if the data suggest important relationships.

9) Privacy, Confidentiality and Data Security

Standard institutional practices will be followed as described in the OHSU Information Security and Research Data Resource Guide to maintain the confidentiality and security of data collected in this study. Study staff will be trained with regard to these procedures.

All scales will be de-identified and a participant number will be assigned to each scale for data management. All data will be kept on the limited-access drives or computers at OHSU or in a locked location in the OHSU ADRC. Documents used for the intervention may be stored with the interventionist and RA in a secure location in the staff member's home. All documents will be shredded or returned to the OHSU ADRC at the completion of the intervention. These documents will not contain any PHI, but will contain the participant's study ID #.

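### The optional race-by-rurality ANOVA takes non-significance as its hypothesis, which at most 20 Care Partners and no equivalence margin cannot turn into evidence of equal efficacy

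*Combined protocol and SAP*

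**What the plan says.** The efficacy text in section 8 (Data Analysis, Phase 2) opens with the main assessment: "Efficacy will be assessed by measuring pre/post changes on the RMBPC". A later paragraph adds an optional subgroup analysis. It begins "Using ANOVA, we may assess pre-post changes in the RMBPC (reactivity subscale", names the comparison as "between four groups (rural White, African American; urban African American, White", and completes the sentence "with the hypothesis that there are no significant differences across groups". The next sentence adds a second optional analysis: "We may test whether the efficacy of our intervention differs across racial and ethnic groups using interaction terms".

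Section 5a sets the size: "We will conduct STELLA-FTD with up to 20 FTD family Care Partners". Section 2, Aim 3, describes the purpose modestly: "Assess the preliminary efficacy of STELLA-FTD on the primary outcomes".

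The document gives no equivalence margin, significance level, SD of the change score, power or precision calculation, minimum cell size, or recruitment target by race or rurality.

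**The concern.** The stated hypothesis is the null of the test that will examine it. More exactly, it is that the test will come out non-significant. Any p-value above the threshold satisfies it, whether the groups truly change alike or the study is too small to tell.

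This reverses the usual effect of low power. Normally a small sample works against the investigators' hypothesis. Here it works in favour, so fewer participants, more dropout or more uneven groups all make apparent confirmation more likely.

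At stake is a possible statement that STELLA-FTD works alike across race and rurality. The document does not say such a statement will be made. But the hypothesis stands next to a sentence asking whether efficacy differs by race and ethnicity, so a non-significant result could easily be read that way.

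**Working it through.** The plan gives no figure to reproduce, so the check asks how often the hypothesis would be met when the groups really differ.

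**Inputs from the document.** Four groups (section 8). At most 20 Care Partners (section 5a), so at best 5 per cell. Phase 1 was 86% White (n=14 reporting) and 14% rural (Table 1).

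**Assumptions, because the document is silent.** Alpha 0.05; a common SD of the change score, set to 1; both African American cells differ from both White cells by *d* SD; 16 analysable as an illustration of dropout; 14/3/2/1 (urban White, urban African American, rural White, rural African American) as an illustrative uneven split.

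**Step 1: chance of a non-significant ANOVA.** The F statistic has 3 and N−4 degrees of freedom and noncentrality λ = Σ nᵢ(μᵢ − μ̄)². With two racial groups *d* apart this becomes λ = N·p(1−p)·d², where p is the African American share. Critical values are 3.24 (N=20) and 3.49 (N=16).

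| Cells | d | λ | Non-significant |
|---|---|---|---|
| 5/5/5/5 | 0 | 0 | 95.0% |
| 5/5/5/5 | 0.5 | 20×0.25×0.25 = 1.25 | 88.5% |
| 5/5/5/5 | 0.8 | 20×0.25×0.64 = 3.2 | 76.5% |
| 5/5/5/5 | 1 | 20×0.25×1 = 5 | 64.6% |
| 4/4/4/4 | 1 | 16×0.25×1 = 4 | 73.1% |
| 14/3/2/1 | 1 | 20×0.2×0.8×1 = 3.2 | 76.5% |

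The first row is simply 1 − alpha; it is there for comparison. In terms of Cohen's f (λ = N·f²), power at N=20 is 11.5% for f=0.25 and 23.5% for f=0.40. If only one of four equal cells differs by 1 SD, power is 27%, so the test is non-significant about 73% of the time.

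**Step 2: precision.** The 95% confidence interval half-width for a difference between two cells is t(0.975, N−4)·√(1/n₁+1/n₂).
- 5 per cell: 2.120 × √(2/5) = 1.34 SD.
- 4 per cell: 2.179 × √(2/4) = 1.54 SD.

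An observed difference of exactly zero would still leave a true difference of 1 SD inside the interval.

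**Step 3: how realistic 5 per cell is.** Suppose Phase 2 had the Phase 1 mix, with race and rurality independent and all non-White participants counted as African American. The expected cells out of 20 are then:
- urban White: 20×0.86×0.86 = 14.8
- rural White: 20×0.86×0.14 = 2.4
- urban African American: 20×0.14×0.86 = 2.4
- rural African American: 20×0.14×0.14 = 0.4

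The last cell is empty with probability (1 − 0.0196)²⁰ = 67%. The balanced design is therefore the favourable case.

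**Step 4: would a margin repair it?** Take an equivalence test (two one-sided 5% tests) with truly equal groups and 16 pooled degrees of freedom. By simulation, for two cells of 5, power is 78% at a margin of 1.90 SD and 81% at 1.95 SD. For the two racial groups (10 v 10), it is 79% at 1.35 SD and 82% at 1.40 SD. Reaching 80% thus takes a margin of about 1.9 SD or 1.4 SD respectively. For comparison, the normal approximation 2·((1.645+1.282)/margin)² gives 18 per group for a margin of 1.0 SD. Four groups would need 72 in all, before allowing for several pairwise comparisons.

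**The case against.** The strongest reply is that little depends on this sentence. The ANOVA is one of several analyses the plan says may be done, in a feasibility study whose efficacy aim is already called preliminary. No decision rule or reporting commitment is attached. The phrase may only record what the investigators expect, and the following sentence poses the subgroup question openly. The hypothesis also cites a source that cannot be examined here, which may explain the expectation. All this is fair and limits the severity. It does not make the hypothesis testable: if the ANOVA is run, non-significance meets a prespecified hypothesis. The interaction test that follows is also a difference test on the same few people, and it supplies no margin.

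A second reply is that 5 per cell is unrealistic and that the more basic difficulty is sparse or empty cells. That is right, but it strengthens the point, since uneven cells raise the chance of a non-significant result.

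A third is that, without a comparator, differences in pre-post change are not strictly differences in efficacy. That also stands. Efficacy is the protocol's own word, and the replacement text can cover both readings.

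**Conclusion.** The concern holds, at minor severity. As worded, the hypothesis would be met more often than not even if the racial groups differed by a full SD of change: 65% of the time in the balanced best case, 73% with 16 analysable, and 76% with the uneven split. A non-significant result would therefore say little about equal efficacy.

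The percentages depend on the assumed alpha, common SD and cell sizes. The conclusion does not depend on any one of them, because non-significance without a margin does not show equality at any sample size. Only this optional subgroup statement is affected.

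**What to change.** In section 8, replace the hypothesis clause of the ANOVA sentence with wording such as:

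> Comparisons across race and rurality groups are exploratory. Differences in RMBPC reactivity change will be reported as estimates with 95% confidence intervals where group sizes allow, and a non-significant difference will not be read as equal change or equal efficacy.

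The ANOVA may stay under that label. Adding an equivalence margin is not a workable alternative, since the margins this sample could support are too wide to be informative.

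The cost is one clause. Recruitment, data collection and the main pre-post analysis do not change. All that is given up is the option of presenting a non-significant result as confirmation.
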